6. OBJECTIVES AND OUTCOME MEASURES

Objectives	Outcome Measures	Timepoint(s) of evaluation of this
		outcome measure
		(if applicable)

Primary Objective		
The effect of one week of CPAP	Continuous interstitial glucose	Nights 5, 6, 7 of
withdrawal versus continued CPAP	measurements from 12 midnight to 7am	each arm.
on continuous interstitial glucose	overnight for each treatment arm	
levels overnight		
Secondary Objectives		
The effect of one week of CPAP	Continuous interstitial glucose	Days and nights 5,
withdrawal versus continued CPAP	measurements during 24 hours for each	6, 7 of each arm.
on other derivatives from	treatment arm	
continuous nocturnal and 24-hour		
interstitial glucose levels, such as the		
mean glycaemic excursions		
Exploratory objectives		
The effect of CPAP withdrawal on	Blood fructosamine levels	Follow-up visit each
average glucose levels		arm
The effect of CPAP on withdrawal on	Morning blood cortisol levels	Baseline and
cortisol levels		follow-up clinic
		visits
The effect of one week of CPAP	Overnight pulse oximetry from during	Nights 5, 6 and 7 of
withdrawal versus continued CPAP	sleep for each treatment arm	each arm.
on the overnight oximetry		

[figure not shown]
7. STUDY DESIGN

The study is a single tertiary-centre, crossover, randomised controlled trial to evaluate the effects of CPAP withdrawal versus continued CPAP on overnight interstitial glucose levels and other measures of cardiovascular risk, OSA severity, and daytime symptoms in patients with CPAP-treated obstructive sleep apnoea and T2DM (not on insulin therapy) or "prediabetes", following withdrawal of CPAP for 7 days.

Data will be collected using a continuous glucose monitor which is a semi-invasive way of monitoring interstitial glucose levels at home over the whole of the day and night up to a maximum period of 10 days. This method of monitoring glucose levels has been chosen because it allows monitoring of overnight glucose levels in a "real-world" setting. Alternative means of monitoring overnight glucose levels would

require hospital admission, intravenous cannulation and frequent blood draws during sleep. In addition, overnight oximetry will be measured at home along with other markers of cardiovascular disease. A blood test will be taken at the screening visit to screen for the presence of undiagnosed diabetes. Further blood tests will be taken at visits 1, 2, 3 and 4 to measure fasting glucose and insulin levels to establish if CPAP withdrawal affects these measures. Subjective sleepiness will be recorded by a questionnaire at screening and visits 1, 2, 3, and 4.

The trial consists of a consent visit which will also be the screening visit, a randomisation visit which also forms the first study visit (visit 1) and three subsequent trial visits following randomisation (visits 2, 3, and 4). Screening consists of one week of pulse oximetry while on CPAP for 3 nights and off CPAP for 4 nights. Following screening, there will be at least 14 days, and no more than 12 weeks, back on CPAP prior to the randomisation visit. Following the randomisation visit participants will then use either sham CPAP or continued therapeutic CPAP for 7 days. They will be placed back onto their own CPAP for at least 14 nights before crossing over. There will be four study visits within 18 weeks of the start of screening. Details of the study visits are shown below in the study flow diagram:

Study flow diagram. CGM=Continuous glucose monitoring, CPAP=continuous positive airway pressure, ESS=Epworth sleepiness score,

8. PARTICIPANT IDENTIFICATION

8.1. Study Participants

Adult participants with OSA of moderate to severe severity and either T2DM not on insulin therapy or "prediabetes" who have been effectively treated with CPAP for over 3 months with good compliance with therapy (mean >6 hours/night).

8.2. Inclusion Criteria

- Participant is willing and able to give informed consent for participation in the trial.
- Male or Female, aged 18 years or above.
- Objectively confirmed obstructive sleep apnoea (at the time of original diagnosis) with an oxygen
 desaturation index (ODI ≥4% dips) of >20/h or/and an apnoea/hypopnoea index of >20/hour (this
 threshold will exclude subjects with borderline OSA, in whom there may be little treatment effect).
- Type 2 diabetes mellitus or HbA1c ≥6.0% (42mmol/l) at screening visit.
- In the Investigator's opinion, is able and willing to comply with all trial requirements.
- Willing to allow his or her General Practitioner and consultant, if appropriate, to be notified of participation in the trial.
- Currently >20/h oxygen desaturations (≥4% dips) returning on any night during a screening period
 of ambulatory nocturnal pulse oximetry performed during a 4-night period without CPAP.
- Treated with CPAP for more than 3 months, minimum compliance 6h per night, where available
 an AHI <10 with treatment (according to machine download data), and ODI < 10 confirmed on
 CPAP during screening oximetry.

8.3. Exclusion Criteria

The participant may not enter the trial if ANY of the following apply:

- Diabetes mellitus requiring treatment with regular insulin therapy.
- Previous ventilatory failure (awake resting arterial oxygen saturation <93% or known arterial $PCO_2 > 6kPa$) or severe respiratory disorders other than OSA.
- Unstable, untreated coronary or peripheral artery disease, severe arterial hypertension (>180/110mmHg), severe arterial hypotension (<90/60mmHg).
- Poorly controlled diabetes with HbA1c ≥10.0% (86mmol/mol).
- Unstable diabetic retinopathy requiring or currently undergoing specialist treatment.
- Previously diagnosed with Cheyne-Stokes breathing.
- Current professional driver or vigilance critical occupation.
- Any sleep-related accident.
- Mental or physical disability precluding informed consent or compliance with the protocol.
- Non-feasible trial follow-up (for example, distance from follow-up centre, physical inability).

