9.3. Screening and Eligibility Assessment

Potentially eligible participants that are interested will be invited to meet with the research team on a screening visit. Exclusion and inclusion criteria will be reviewed and informed consent will be obtained prior to any trial specific procedures as described above. Participants will then undergo ambulatory nocturnal pulse oximetry for 7 nights. The first three nights are carried out on the participants' normal CPAP therapy to confirm adequate control with an ODI < 10 events/ hour. The participant is then taken off CPAP therapy for 4 nights with oximetry monitoring on all four nights. A return of > 20/h oxygen desaturations (≥4% dips) on any of the 4 nights confirms that sufficiently severe OSA has returned to satisfy the entry criteria. Manual editing for clear awake periods or clear periods of artefact will be allowed at the discretion of the investigator.

The initial phase of the study where CPAP is withdrawn for 4 nights provides additional interesting data, as not all patients do experience a return of OSA in that time period. Those that do not experience a return

of OSA do not enter the main study, however this data will be retained to try and understand why some patients relapse quickly on withdrawal and others do not.

At the screening visit, participants will have a blood test to measure HbA1c levels to confirm eligibility (HbA1c ≥6.0% (42mmol/l) at screening visit). This procedure is described in more detail later. Participants will not need to be fasted prior to this assessment. Participants will be contacted by telephone prior to stopping their CPAP therapy if they are not eligible on the basis of their HbA1c. Data from the first three nights of oximetry recordings on CPAP will provide useful clinical data ensuring they are on the correct CPAP settings. Data from these recordings will be passed on to the clinical team for onwards clinical care.

Following the screening week eligible participants resume their CPAP therapy for at least 14 days and no more than 12 weeks prior to randomisation. Participants eligible for entry into the study will then be contacted by the research team to arrange randomisation and subsequent study visits.

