In addition, participants' demographic, past medical history, medications and eligibility criteria will be assessed. Participant's height, weight and neck circumference will be recorded. Data from participants' own CPAP machine will be downloaded to ensure an average use of CPAP of >6 hours/night over all days in the last 30 days prior to the screening visit.

Rescreening will be allowable only for participants in whom there is a technical failure in a screening procedure or participants with an on-CPAP ODI of >10 events/hour on any of three nights. In the case of a technical failure, there are no time constraints for when rescreening can be repeated. In the case of an ODI > 10 events/hour rescreening can be repeated following adjustments to participants' CPAP therapy and at least 14 nights on this adjusted CPAP therapy. Only assessments with technical failure will be repeated (e.g. overnight pulse oximetry or HbA1c measurements) and a maximum of two rescreening attempts will be allowed.

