9.7. Baseline Assessments

Participants will attend for Visit 1 at least 14 days and no more than 12 weeks from their screening visit. Eligibility criteria will be checked including screening oximetry and HbA1c levels.

Participants will need to have fasted for 8 hours prior to this visit.

First, participants will have their office blood pressure and heart rate recorded in triplicate following at least 5 minutes of rest in a seated position from their left arm. At least one minute will be allowed between each blood pressure measurement.

Second, participants will have blood tests taken, totalling a maximum of 35ml (around two tablespoonsful). These will be sent for glucose levels, insulin levels, full blood count, urea, creatinine and electrolytes, lipid profile and for plasma/serum storage for markers of cardiovascular disease.

Participants will be requested to complete an Epworth sleepiness score, an eight-point questionnaire.

At Visit 1 the researcher will supply the participant with a continuous glucose monitor (Dexcom G6®) sensor and transmitter as described in the procedures section. Participants will have this process repeated at Visit 3 after crossing over.

Clinical Research Protocol Template version 15.0

CONFIDENTIAL

At Visit 1 participants will be supplied with pulse oximetry (Minolta 300i). Every night, oxygen saturation measurements (and pulse rate rises) will be performed at home using this simple overnight pulse oximeter. Participants will have this process repeated at Visit 3 after crossing over.

Data from participants' CPAP machine will be downloaded for an average use of CPAP over all days in the last 14 days prior to the visit. This will not be assessed as an eligibility criterion as this will have already been assessed at the screening visit (see section 9.3).

Eligibility criteria will be checked prior to randomisation. Participants will then be supplied with a new CPAP machine, either therapeutic or sham. The participant's own CPAP machine will be collected and securely stored until Visit 2.

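### No blood pressure reading is scheduled before the 4-night CPAP withdrawal at screening, so unrecognised pressure above 180/110 mmHg is found only at Visit 1

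*Protocol*

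**What the plan says.** Section 8.3 lists "severe arterial hypertension (>180/110mmHg" among the conditions that bar entry to the trial.

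Section 9.3 describes the screening visit. Of eligibility it says "Exclusion and inclusion criteria will be reviewed and informed consent will be obtained prior to any trial specific procedures as described above". Three nights of oximetry on CPAP follow, and then "The participant is then taken off CPAP therapy for 4 nights with oximetry monitoring on all four nights". On physical measurements the section says only "Participant's height, weight and neck circumference will be recorded". The procedures table in section 9 agrees: the row for clinic blood pressure and heart rate is marked at Visits 1, 2, 3 and 4 and is empty at Screening, while the eligibility row is marked at both Screening and Visit 1.

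The first scheduled reading is in section 9.7, at Visit 1, where "participants will have their office blood pressure and heart rate recorded in triplicate following at least 5 minutes of rest". The same section adds "Eligibility criteria will be checked prior to randomisation".

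**The concern.** A numeric limit can be confirmed only by measurement, and here the first scheduled measurement comes after the first CPAP withdrawal. Review of the criteria and the medical history at screening will exclude a patient known to be above 180/110 mmHg. It will not find one whose pressure is unrecognised or has recently gone out of control.

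The stake is patient safety. Section 10.5 names a rise in blood pressure as an expected effect of withdrawal, and section 10 collects serious adverse events from the Screening Visit onward. A patient above the limit would spend 4 nights off CPAP for a trial that this patient cannot enter. The protocol does not say why the limit exists; that it is partly protective is an inference.

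**Working it through.** The point turns on the order of procedures, so the sections are set side by side.

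**Order of events as written**

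1. Screening visit (9.3): consent, criteria review, history, medications, body measurements, HbA1c, CPAP download. No blood pressure reading is scheduled.
2. Three nights of oximetry on CPAP (9.3).
3. Four nights of oximetry off CPAP (9.3).
4. Return to CPAP (7 and 9.3).
5. Visit 1 (9.7): first scheduled blood pressure reading, eligibility check, randomisation.

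**Comparison with the rest of the protocol**

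- HbA1c is handled differently. Under 9.3 a patient who is ineligible on HbA1c is telephoned before CPAP is stopped. Blood pressure, which withdrawal is expected to raise, has no such check.
- Each 7-night randomised period has a scheduled reading at its start (Visit 1 or 3) and its end (Visit 2 or 4). The 4-night screening withdrawal has neither.

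**Time from the last off-CPAP night to the first scheduled reading**

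- Section 9.7 says "Participants will attend for Visit 1 at least 14 days and no more than 12 weeks from their screening visit". Taken alone, with a 7-night screening week, the minimum is 14 − 7 = 7 days.
- Section 7 says "Following screening, there will be at least 14 days, and no more than 12 weeks, back on CPAP prior to the randomisation visit", and 9.3 agrees. The minimum is then 14 days.
- A visit that meets all three sections falls at least 14 days after the last off-CPAP night.

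This interval shows how late the check comes. It is not added exposure, because the patient is back on CPAP by then. The exposure is the 4 nights.

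**Size of the blood pressure effect**

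Section 5 reports rises of 9 mmHg systolic and 7.8 mmHg diastolic in home morning pressure during withdrawal, and describes such withdrawals as typically 2 weeks long. These are group averages. The protocol gives no 4-night figure, so they show direction only.

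**Prior safety record**

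Section 10.5 reports no serious adverse events in over 100 participants in longer withdrawals. Taking 0 events in 100, the one-sided 95% upper bound is 1 − 0.05^(1/100) = 0.0295, about 3.0% per participant. This bound concerns any serious event in those participants. The protocol does not say whether any of them was severely hypertensive, so it neither establishes nor excludes a risk in that group.

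**Time cost of a reading**

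The method in 9.7 is 5 minutes of rest, then three readings at least 1 minute apart: 5 + 2 × 1 = 7 minutes at minimum.

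**The case against.** The strongest reply is that the limit is enforced where it matters most. It bars entry to the trial, 9.3 separates the initial withdrawal phase from the main study, and blood pressure is measured before randomisation. There are also two earlier filters: the clinical team applies the eligibility criteria when identifying patients (9.1), and the criteria are reviewed again at the screening visit (9.3). Nothing stops the investigator from taking a reading then. Section 16.4 says two-week withdrawals have been safe in earlier trials, and both that section and the lay summary note that patients stop CPAP for short periods anyway. The subgroup is unquantified and probably very small.

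Much of this stands. The randomised nights are covered, no two sections contradict each other on this point, and the primary estimate is unaffected. It is also correct that the gap concerns scheduled readings only, and that the 3.0% bound is not specific to severe hypertension.

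It does not remove the gap. The two filters can find only hypertension already on record, unless someone takes a reading that the protocol does not ask for; neither section requires a recent value on file. The reassuring experience is not described for patients above 180/110 mmHg. The off-CPAP nights at screening are a trial procedure, whatever name that phase is given.

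**Conclusion.** The concern holds. Followed as written, the protocol puts the first measured check of the 180/110 mmHg limit after the first CPAP withdrawal. An affected patient has 4 nights off CPAP before any scheduled reading.

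The size is modest. Only patients above the limit with no record of it are affected; their number cannot be derived from the protocol and is likely small. The clinical consequence of 4 nights is not quantified either. The order of events is certain from the text; the harm is an inference from the protocol's own expectation that withdrawal raises blood pressure. The change should be made because the exposure is avoidable at almost no cost. The trial's validity is not in question.

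**What to change.** In the section 9 procedures table, add a Screening mark to the row for clinic blood pressure and heart rate. In 9.3, add a sentence such as: *Clinic blood pressure is recorded in triplicate at the screening visit as in 9.7, and the 8.3 blood pressure limits are confirmed before CPAP is stopped.* Keep the Visit 1 reading as the re-check before randomisation. The wording also covers the lower limit of 90/60 mmHg in 8.3, although the concern here is the upper one.

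The cost is one table mark, one sentence and about 7 minutes per screened patient. Section 9.8.1 already requires the screening visit to be face-to-face. No threshold, endpoint or sample size changes.

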9. PROTOCOL PROCEDURES

Procedures	Screening	Visit 1	Visit 2	Visit 3	Visit 4	Daily during trial
Informed	Х					
consent	^					
Demographics	X					
Medical	Х					
history	^					
Fasting blood						
glucose (8		Χ	X	Х	Х	
hours)						
HbA1c level	X					
CPAP	Х		Х		Х	
download	^		^			
Eligibility						
assessment						
(includes 7	Х	Χ				
nights of pulse						
oximetry)						
Continuous						
glucose		Xa				X
monitoring						
Randomisation		Χ				
Laboratory		Х	Х	Х	Х	
tests (blood)		۸	^	^	^	
Clinic blood						
pressure and		Χ	Х	Х	Х	
heart rate						
ESS	Х	Х	Х	Х	Х	
(questionnaire)	^	^	^	۸	۸	
Overnight						
Pulse	X					X
oximetry*						

a) continuous glucose monitor supplied and fitted at visits 1 and 3. This will then continually record throughout the trial until it is collected at visits 2 and 4.

9.1. Recruitment

Participants will be recruited from database records of patients with OSA treated with CPAP at the Oxford Centre for Respiratory Medicine and from patients attending routine clinical appointments with the Oxford Centre for Respiratory Medicine.

^{*} every night during the trial starting the night after visit 1 (not including washout)

Potential participants will be identified for trial enrolment according to the eligibility and ineligibility criteria outlined by members of the clinical team. Participants will be contacted by letter sent by a member of the clinical team on behalf of the research team. A Patient Information Sheet and Consent Form will be enclosed for patients to read at home. Patients will have an option to send off a reply slip or email/phone the study team to confirm they wish to or do not wish to be contacted by the research team. If no response is received within three weeks, the letter will be followed up by a phone call from the clinical team. Patients interested in taking part in the trial will be invited for a screening/enrolment visit.

In addition, patients enrolled in the Oxford Respiratory Research Register who had consented to being approached directly about future research trials will be directly approached by the research team, initially by invitation letter as outlined above.

9.2. Informed Consent

The participant must personally sign and date the latest approved version of the Informed Consent form before any trial specific procedures are performed.

Written and verbal versions of the Participant Information and Informed Consent will be presented to the participants detailing no less than: the exact nature of the trial; what it will involve for the participant; the implications and constraints of the protocol; the known side effects and any risks involved in taking part. It will be clearly stated that the participant is free to withdraw from the trial at any time for any reason without prejudice to future care, without affecting their legal rights and with no obligation to give the reason for withdrawal.

The participant will be allowed as much time as wished to consider the information, and the opportunity to question the Investigator, their GP or other independent parties to decide whether they will participate in the trial. Written Informed Consent will then be obtained by means of participant dated signature and dated signature of the person who presented and obtained the Informed Consent. The person who obtained the consent must be suitably qualified and experienced, and have been authorised to do so by the Chief/Principal Investigator. A copy of the signed Informed Consent will be given to the participant. The original signed form will be retained at the trial site.

9.3. Screening and Eligibility Assessment

Potentially eligible participants that are interested will be invited to meet with the research team on a screening visit. Exclusion and inclusion criteria will be reviewed and informed consent will be obtained prior to any trial specific procedures as described above. Participants will then undergo ambulatory nocturnal pulse oximetry for 7 nights. The first three nights are carried out on the participants' normal CPAP therapy to confirm adequate control with an ODI < 10 events/ hour. The participant is then taken off CPAP therapy for 4 nights with oximetry monitoring on all four nights. A return of > 20/h oxygen desaturations (≥4% dips) on any of the 4 nights confirms that sufficiently severe OSA has returned to satisfy the entry criteria. Manual editing for clear awake periods or clear periods of artefact will be allowed at the discretion of the investigator.

The initial phase of the study where CPAP is withdrawn for 4 nights provides additional interesting data, as not all patients do experience a return of OSA in that time period. Those that do not experience a return

of OSA do not enter the main study, however this data will be retained to try and understand why some patients relapse quickly on withdrawal and others do not.

At the screening visit, participants will have a blood test to measure HbA1c levels to confirm eligibility (HbA1c ≥6.0% (42mmol/l) at screening visit). This procedure is described in more detail later. Participants will not need to be fasted prior to this assessment. Participants will be contacted by telephone prior to stopping their CPAP therapy if they are not eligible on the basis of their HbA1c. Data from the first three nights of oximetry recordings on CPAP will provide useful clinical data ensuring they are on the correct CPAP settings. Data from these recordings will be passed on to the clinical team for onwards clinical care.

Following the screening week eligible participants resume their CPAP therapy for at least 14 days and no more than 12 weeks prior to randomisation. Participants eligible for entry into the study will then be contacted by the research team to arrange randomisation and subsequent study visits.

In addition, participants' demographic, past medical history, medications and eligibility criteria will be assessed. Participant's height, weight and neck circumference will be recorded. Data from participants' own CPAP machine will be downloaded to ensure an average use of CPAP of >6 hours/night over all days in the last 30 days prior to the screening visit.

Rescreening will be allowable only for participants in whom there is a technical failure in a screening procedure or participants with an on-CPAP ODI of >10 events/hour on any of three nights. In the case of a technical failure, there are no time constraints for when rescreening can be repeated. In the case of an ODI > 10 events/hour rescreening can be repeated following adjustments to participants' CPAP therapy and at least 14 nights on this adjusted CPAP therapy. Only assessments with technical failure will be repeated (e.g. overnight pulse oximetry or HbA1c measurements) and a maximum of two rescreening attempts will be allowed.

